## 1. Introduction

### 1.1 Study Foundation

Breast cancer claims 40-250% more African-American lives compared to White and Asian-Americans and is the most frequent cause of cancer deaths in Hispanics/Latinas. Breast cancer is diagnosed at later stages in African-Americans and Latinas suggesting persistent disparities in care delivery by race/ethnicity. Participation in clinical trials by women of color (WOC, which is defined as non-white women for the purposes of this study) is needed to improve outcomes, reduce health inequity and increase trial generalizability. Disappointingly, within ECOG-ACRIN, WOC participation remains less than 10% regardless of trial type (therapeutic, diagnostic/ surveillance or screening). Improving clinical trial participation among WOC is therefore a high priority to ensure that trial results are truly generalizable to women of all racial/ethnic groups.

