### 1.2 Background

In EA1151 Tomosynthesis Mammographic Imaging Screening Trial (TMIST), a randomized controlled trial of digital mammography (DM) vs tomosynthesis (TM) to evaluate stage shift in screen-detected cancers, participation by Asians and Hispanics in particular have lagged. Cost concerns are a known barrier to trial participation disproportionately affecting WOC. The COVID-19 pandemic will likely worsen trial participation among WOC. Unfortunately for many women, participation in TMIST can result in out-of-pocket costs since commercial insurance coverage of TM is widely variable. Concerns about study-related costs are a known barrier to trial participation and the COVID-19 pandemic has resulted in record unemployment and insurance loss that has disproportionately affected minorities.

The economic toll can be broadly considered as financial hardship which has two main components, 1) material condition referring to actual financial resources available, and 2) psychological response to their material condition (see model). This financial hardship will further constrain many participants' financial resources (material condition) and ability to afford out-of-pocket expenses associated with trial participation and may lead to financial distress (representing the psychological response), preferentially affecting WOC who decline participation compared to non-WOC who decline. Additional federal-, state- and local-level factors (e.g., shelter-in-place policies, local unemployment during COVID-19) may also contribute to trial nonparticipation (Fig 1). COVID-19 is a natural experiment to compare the role of financial hardship on willingness to participate in clinical trials between WOC and non-WOC and any widening of disparities in WOC trial participation in TMIST. This observational ancillary study results will be used to inform future trials of interventions to improve trial participation among WOC, e.g., financial assistance and financial navigation services for trial-related expenses.

In a population of women who decline participation in TMIST (EAQ201 participants), we plan to compare the proportion of WOC who experience COVID-related change in their material condition (income/employment/insurance loss) vs non-WOC. Secondary and exploratory analyses will compare the proportions of WOC vs non-WOC with other person-level COVID-related factors

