
TABLE 1 : Participant-completed items	
Primary Endpoints	Measure (collected from EAQ201 participants)
COVID-related financial hardship among EAQ201 participants	Composite outcome, defined as answering in the affirmative to any of the following personal changes due to COVID: layoff or furlough, insurance loss, work hours reduction, new job/increased hours to increase income, food or housing insecurity (items used in EAQ162CD) OR answering in the affirmative to any of the following household changes due to COVID: ≥20% income loss, savings use for living expenses, home sale/refinance, increased debt, declared bankruptcy (items used in EAQ162CD)
Secondary Endpoints	Collected from EAQ201 participants
Material condition composite measure	Self-reported material condition of any of the following: >20% income loss, savings use, home sale or refinance, loans, reaching credit limits, becoming subject to a collection agency, or bankruptcy in the last 3 months (binary) (1 item, used in EAQ162CD)
COVID-specific perceived financial distress	Adapted from the summary item from COST measure.  (continuous) “COVID-19 has been a financial hardship to my family.” (1 item)
Exploratory Endpoints	Collected from EAQ201 participants
Employment change	Self-reported work hours reduction, layoff or furlough, sick time or vacation time use or new job/increased hours to increase income (binary) (1 item, used in EAQ162CD)
COVID-specific perceived distress	Adapted from [name] (personal communication) to capture the emotional response to COVID related to fear of infection, financial anxiety, housing and food insecurity (single items). (categorical)(11 items)
Perceived susceptibility to disease	Single items for breast cancer and COVID-19, modified from previous studies of intention to undergo breast cancer screening and used in EA2185 and EAQ162CD. (categorical) (2 items)
Distress coping behavior that increase breast cancer risk	We previously demonstrated that risky behaviors (e.g., cancer screening adherence, not smoking and seatbelt use  ). Alcohol  use has been described a risk factor for breast cancer. Smoking  has been raised as a risk factor. We will assess change in frequency or amount of tobacco or alcohol use during COVID compared to before COVID. We will not assess absolute amount of use. (categorical) (2 items)

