7.2 Primary Objective

The primary objective is to compare the proportion of WOC EAQ201 participants who experience COVID-related financial hardship vs non-WOC EAQ201 participants. The results, with and without adjustment for missing values (see [7.5](#)), will be compared as a sensitivity analysis. Logistic regression models, with and without stratification by WOC status, will be fit with financial hardship as the response variable to investigate other sociodemographics (e.g., age, marital status, insurance status) and state- and local-level factors (e.g., state COVID severity, shelter-in-place policies, state and local unemployment during shelter-in-place) as moderators.

Sample Size Considerations for the Primary Objective ([7.1.1](#)):

The primary objective is to compare the proportion of WOC EAQ201 participants who experience COVID-related financial hardship (see **Table 1** for definition) with the proportion of non-WOC EAQ201 participants who experience COVID-related financial hardship. The National Bureau of Economic Research estimated unemployment rates by race and ethnicity in April 2020, around shelter-in-place regulations. Unemployment in African-American and Latinx populations averaged 18% compared to Whites (13%). At a sample size of 1000 women who decline TMIST participation, we expect to recruit at least 10-25% WOC into this study. Assuming alpha of 0.05, we estimated power over a range of differences across various proportions (see **Table 4**). For instance, at a sample size of 1000 with 10% of WOC, we have 77% power to detect a minimum difference of 0.10 between two proportions (0.2 vs. 0.1); at a sample size of 1000 with 25% of WOC, we have 88% power to detect a minimum difference of 0.08 between two proportions (0.18 vs. 0.1). Please note that based on DCP-001, 16% of the women who declined TMIST were WOC. Accrual onto TMIST is expected to continue for another 4.4 years. Also based on DCP-001 and extrapolating to the Non-NCORP US sites, accruing 1,000 women to this study is achievable. We do not envision any danger that this study will close due to lack of accrual.

**Table 4: Estimated power for a two-sample proportions using Fisher's Exact test (two-sided). N1: # of WOC; N2: # of non-WOC**

Sample size (N)	N1/N2	P1 (WOC)	P2 (non-WOC)	Delta	Alpha	Power
(Sample size: 1000; N1/N2=1/9, i.e.,10% of WOC)						
1000	1/9	0.200	0.100	0.100	0.05	0.77
1000	1/9	0.225	0.100	0.125	0.05	0.90
1000	1/9	0.250	0.100	0.150	0.05	0.96

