## 7.6 Gender and Ethnicity

Based on TMIST data from participants enrolled in September 2020, at sites in the United States, the anticipated accrual in subgroups defined by gender and race is:

Racial Categories	Not Hispanic or Latino Female	Not Hispanic or Latino Male	Hispanic or Latino Female	Hispanic or Latino Male	Total
American Indian/ Alaska Native	2	0	0	0	2
Asian	19	0	0	0	19
Native Hawaiian or Other Pacific Islander	1	0	0	0	1

Racial Categories	Not Hispanic or Latino Female	Not Hispanic or Latino Male	Hispanic or Latino Female	Hispanic or Latino Male	Total
Black or African American	196	0	2	0	198
White	742	0	30	0	772
More Than One Race	6	0	2	0	8
Total	966	0	34	0	1,000

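### Does section 7.2 overstate power because no row of Table 4 uses the 18% vs 13% disparity it cites?

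*Combined protocol and SAP*

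**What the plan says.** Section 7.2 motivates the primary comparison with a national labor statistic: "Unemployment in African-American and Latinx populations averaged 18% compared to Whites (13"%). It then says that power was estimated for a range of differences and proportions, and gives two examples from Table 4. For 10% WOC, "we have 77% power to detect a minimum difference of 0.10 between two proportions (0.2 vs. 0.1"). For 25% WOC, "we have 88% power to detect a minimum difference of 0.08 between two proportions (0.18 vs. 0.1"). Table 4 specifies a two-sided Fisher's exact test at alpha 0.05 with N = 1000. Its non-WOC rates are 0.10 and 0.15, and its gaps run from 0.08 to 0.15.

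On the WOC share, the same section notes that "based on DCP-001, 16% of the women who declined TMIST were WOC". Section 7.6 projects accrual from TMIST participants, not decliners, and puts 228 of 1,000 women outside the White row.

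Table 1 (section 5) defines the endpoint as a yes to any listed item. The personal items are "layoff or furlough, insurance loss, work hours reduction, new job/increased hours to increase income, food or housing insecurity". The household items are income loss of at least 20%, use of savings, home sale or refinancing, increased debt and bankruptcy.

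**The concern.** The text moves from 18% against 13% to powers of 77% and 88% within a few sentences, so a quick reader could attach those powers to that disparity. Three features encourage this.

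- The cited gap is smaller than every row of Table 4 on each scale. It is 5 points, odds ratio 1.47 and risk ratio 1.38; the smallest values in the table are 8 points, 1.69 and 1.53.
- The 25% WOC example uses 0.18, the same value as the cited African-American and Latinx rate, but sets it against 0.10.
- Section 7.2 gives no expected prevalence or gap for the composite and no source for 0.10 or 0.15.

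If the hardship gap really were 18% against 13%, 1,000 women would miss it in roughly 53-73% of repetitions across 10-25% WOC. Section 1.2 says the "results will be used to inform future trials of interventions to improve trial participation among WOC", so a null result wrongly read as no disparity would carry weight.

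**Working it through.** **Inputs.** N = 1000, alpha 0.05 two-sided, Fisher's exact test, WOC shares of 10% and 25% (Table 4); 16% among decliners, and the pair 18% and 13% (section 7.2).

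**1. Reproduce the plan's figure (0.18 vs 0.10, 250 vs 750).** A continuity-corrected normal approximation can be followed by hand.
- Pooled rate: (45 + 75)/1000 = 0.12.
- Null SE: sqrt(0.12 × 0.88 × (1/250 + 1/750)) = 0.02373.
- Alternative SE: sqrt(0.18 × 0.82/250 + 0.10 × 0.90/750) = 0.02665.
- Correction: 0.5 × (1/250 + 1/750) = 0.00267.
- z = (0.08 − 0.00267 − 1.96 × 0.02373)/0.02665 = 1.16, so power is 0.876.

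Exact enumeration of the Fisher test gives 0.886; the plan states 0.88. For 0.20 vs 0.10 at 100 vs 900 the exact value is 0.777; the plan states 0.77. All 12 rows of Table 4 reproduce to within 0.014.

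**2. Put in the cited pair (0.18 vs 0.13, 250 vs 750).**
- Pooled rate: (45 + 97.5)/1000 = 0.1425.
- Null SE 0.02553; alternative SE 0.02722.
- z = (0.05 − 0.00267 − 1.96 × 0.02553)/0.02722 = −0.10, so power is 0.46.

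Exact Fisher: 0.466 at 25% WOC, 0.365 at 16%, 0.266 at 10%. For 80% power at this pair, N would be about 2,200 at 25% WOC and 4,500 at 10%.

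**3. Which part of the mismatch matters?** The bases 0.10 and 0.15 bracket 0.13. Moving only the base to 0.13 and keeping each example's gap gives 0.709 (0.23 vs 0.13, 10% WOC) and 0.828 (0.21 vs 0.13, 25% WOC). The fall in step 2 therefore comes mainly from the 5-point gap.

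**4. Was 0.18 taken from the unemployment figure?** The 25% WOC block adds 0.08, 0.10 and 0.12 to each base: 0.18, 0.20, 0.22 and 0.23, 0.25, 0.27. The 10% block adds 0.10, 0.125 and 0.15 in the same way. On this grid 0.18 is simply 0.10 + 0.08.

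**5. What does the unemployment gap imply for the composite?** The documents do not say, so each line below is an assumption.

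| Assumption | Power |
|---|---|
| 5-point gap held, non-WOC base 13-50% | 0.15 to 0.48 |
| Odds ratio 1.47 held, base 13-70% | at most 0.75 |
| Risk ratio 1.38 held, base 30% | 0.62 at 10% WOC, 0.79 at 16%, 0.90 at 25% |
| Risk ratio 1.38 held, base 50% | at least 0.96 |
| Three independent items, each 18% vs 13% | 0.55 at 10% WOC, 0.72 at 16%, 0.84 at 25% |

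The last line uses 1 − 0.82³ = 0.449 and 1 − 0.87³ = 0.341, a gap of 10.8 points. Complete overlap of the items would bring it back to 18% vs 13%. The range runs from 0.15 to nearly 1, with the stated powers inside it.

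**6. The word minimum.** Table 4 gives 0.66 for a 0.10 gap at 10% WOC (0.250 vs 0.150) and 0.79 for a 0.08 gap at 25% WOC (0.230 vs 0.150). The stated powers thus belong to particular pairs and not to every pair with that gap.

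**The case for a change.** The strongest case for a change is that a range of scenarios ought to include the only disparity the plan cites. If unemployment is a fair proxy, the study is underpowered for it at every planned WOC share; if it is not, the rates in Table 4 have no stated basis. Either way, one sentence and one or two rows would cost almost nothing. The plan's own 16% share also has no row, although 0.18 vs 0.10 there gives 0.774 and not 0.88.

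Much of this stands as description. Section 7.2 does not justify 0.10 or 0.15 and gives no expected composite rate, and the word minimum is loose.

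The step to a defect does not stand. An any-of endpoint with about ten items has no reason to share the rate or gap of one labor-market statistic, and the plan does not say it does. Raising N to 2,200-4,500 would size the study for a target it never set. The worry about a null result concerns how results are reported: nothing in the plan says a non-significant test will be read as no disparity. The primary result is two proportions, from which the difference and its interval follow directly. At 18% vs 13% and 25% WOC, the 95% half-width would be 1.96 × 0.02722 = 5.3 points, enough to show a reader what had not been excluded.

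**Conclusion.** No change follows. Table 4 is a detectable-difference table for a fixed sample of 1,000. Its powers are correct for the pairs it names, and both examples print the pair beside the power. The figures 0.47, 0.37 and 0.27 at 25%, 16% and 10% WOC are also correct, but they are the power for an unemployment contrast and not the study's power for composite hardship. Setting 88% against 47% compares two different quantities.

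The remainder is a gap in explanation, with no source for 0.10 and 0.15 and no expected composite rate, plus the loose word minimum. Neither affects the test, the analysis set or the validity of the estimate, and no stated target is missed. A careful analyst would report the difference with its interval and would not treat a non-significant result as evidence of equality.

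This rests on reading 18% vs 13% as background. If the sponsor meant those figures as the expected endpoint rates, 1,000 women would give 0.27-0.47 power over the planned 10-25% WOC; nothing in the documents says so.

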### 7.3 Secondary Objectives

Two-sample proportion tests (e.g., Z-test based on normal approximations or Fisher's exact test) will be used to compare the proportions of WOC vs non-WOC EAQ201 participants with 1) COVID-related change in their material condition; 2) COVID-specific perceived financial distress. Logistic regressions may be performed to adjust for potential confounders during the comparisons. Missing data will be managed as below (See [7.5](#)).

The proportion of WOC in EAQ201 participants will be compared to the proportion of WOC in TMIST participants using the one-sample proportion test. Based on the TMIST data, the proportion of WOC in TMIST participants is around 25%. Then we will have 80% power to detect a difference of 3.9% using a two-sided exact test with a significant level of 0.05.

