### 2.2 Secondary Objectives

2.2.1 Compare the proportions of WOC vs non-WOC EAQ201 participants with COVID-related change in their material condition, a composite measure.

2.2.2 Compare the proportions of WOC vs non-WOC EAQ201 participants with COVID-specific perceived financial distress.

2.2.3 Compare the proportion of WOC in TMIST participants vs EAQ201 participants. A key hypothesis (now 2.2.3) is that financial hardship preferentially affects WOC and therefore their participation in TMIST. In order, to test this hypothesis, we need to compare the proportion of WOC who participated in TMIST compared to those who declined to participate in TMIST (estimated by EAQ201 participants).

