We will also compare the sociodemographic characteristics of women who complete the EAQ201 participant survey with women who agree to participate in TMIST over the same time period using only data collected as part of the TMIST study that have also been collected as part of the current study. No additional data will be collected from women who participate in the TMIST study.

No additional participant-level data will be collected from TMIST participants related to COVID-19 given the supplement scope. We elected to more completely understand the effects of COVID-19 on those who declined participation in TMIST.

Site characteristics and recruitment process: All sites will receive \$30 per-case reimbursement for each eligible participant who registered to EAQ201. As with EAQ162CD, the study will provide some resources to assist the site, in particular: 1) site RA guides for engaging women who decline TMIST to enhance EAQ201 participation; 2) biweekly webinars/ phone calls for sites to check-in and discuss issues regarding recruitment and/or other study related issues, as needed. Sites that have implemented successful recruitment processes will be encouraged to attend and share their experiences.

Site Recruitment Plan: EAQ201 Study Chair or her designee will present the EAQ201 study to TMIST participating sites via standing TMIST Open Sites calls and through

direct email outreach to site TMIST PIs and lead TMIST research coordinators. This introduction to the study is expected to occur as close as possible to EA activation of the trial. The purpose of the study, site responsibilities, survey team responsibilities, and timeline will be presented on these calls. Along with materials to help support recruitment effort including phone script, study talking points, FAQs to help sites understand the study and to be able to communicate it to potential participants.

All EA1151 participating sites in the United States that are approved to enroll to EA1151 according to CTSU and actively recruiting and enrolling new participants to EA1151 based on at least one new enrollment attributed to the site in the most recent CTSU monthly enrollment report will be cleared to activate EAQ201 by ECOG-ACRIN upon obtaining EAQ201 NCI CIRB approval.

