#### 7.1.2 Secondary Objectives

7.1.2.1 Compare the proportions of WOC vs non-WOC EAQ201 participants with COVID-related change in their material condition, a composite measure.

Hypothesis: Compared to non-WOC, WOC will experience more COVID-related change in their material condition.

7.1.2.2 Compare the proportions of WOC vs non-WOC EAQ201 participants with COVID-specific perceived financial distress.

Hypothesis: Compared to non-WOC, WOC will experience more COVID-specific perceived financial distress.

7.1.2.3 Compare the proportion of WOC in TMIST participants vs EAQ201 participants.

Hypothesis: The proportion of WOC should be higher in the TMIST decliners than that in TMIST agree-ers.

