### 7.4 Assess the effects of sociodemographic characteristics, and federal-, state- or local-level COVID-19 factors on TMIST participation, in WOC vs non-WOC.

For the exploratory objective ([7.1.3.5](#)), we will compare the effects of sociodemographic characteristics, federal-, state- or local-level factors (e.g. maximum number of COVID-19 cases, state unemployment during shelter-in-place, local unemployment during shelter-in-place) on TMIST participation, stratified by WOC vs non-WOC. We will fit a logistic regression model with TMIST participation status (EAQ201 participant or TMIST participant) as the response variable to investigate other sociodemographic (e.g., marital status, neighborhood SES, insurance type), federal-, state- or local-level factors (see **Table 2**). Regression modeling will be conducted with and without stratification by WOC vs non-WOC.

The analysis set will include the 1000 EAQ201 participants from this study and a corresponding number of TMIST participants, who will be randomly selected from the enrolled participants in the main TMIST study. The selection will be stratified by site and enrollment time. Assuming that the proportion of overall EAQ201 participants is from 0.20 to 0.50, **Table 5** below shows the power analysis of testing for the odds ratio in the logistic regression. The variables of interest can be continuous or categorical (binary). For instance, 2000 women (1000 EAQ201 participants versus 1000 randomly selected TMIST participants) achieves 90% power at a 0.050 significance level to detect a change in the proportion of EAQ201 participants from 0.50 at the mean of the testing variable to 0.538 when the value of the variable is increased to one standard deviation above the mean. This change corresponds to an odds ratio of 1.165. An adjustment was made since a multiple regression of the independent variable of interest on other independent variables in the logistic regression obtained an R-Squared of 0.10.

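### The WOC share among decliners is tested against the TMIST share with a one-sample test, as if the TMIST share carried no sampling error, and no TMIST sample size is given for this objective

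*Combined protocol and SAP*

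**What the plan says.** Objective 2.2.3 says the study needs to "compare the proportion of WOC who participated in TMIST compared to those who declined to participate in TMIST", with EAQ201 participants standing in for the decliners. Section 7.1.2.3 repeats it: "Compare the proportion of WOC in TMIST participants vs EAQ201 participants". Section 5 describes the TMIST side of the sociodemographic comparison as "women who agree to participate in TMIST over the same time period", without a number; Table 1 lists race/ethnicity among the TMIST variables.

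Section 7.3 then sets the analysis: "The proportion of WOC in EAQ201 participants will be compared to the proportion of WOC in TMIST participants using the one-sample proportion test". Its planning value is given as "Based on the TMIST data, the proportion of WOC in TMIST participants is around 25" per cent, followed by "Then we will have 80% power to detect a difference of 3.9% using a two-sided exact test" at the 0.05 level. For the other two secondary comparisons, the same section uses a different family: "Two-sample proportion tests (e.g., Z-test based on normal approximations", or Fisher's exact test.

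TMIST sample sizes appear only in section 7.4 and Table 5, for exploratory objective 7.1.3.5. The assumption there reads "Assuming that the proportion of overall EAQ201 participants is from 0.20 to 0.50", and the worked example pairs 1,000 EAQ201 women with 1,000 randomly selected TMIST women.

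**The concern.** A one-sample test is right when the reference proportion is a fixed number. Here the reference is itself estimated from a group of women, so the difference between the two shares has two sources of sampling error and the test counts only one. Three consequences follow.

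- **Type I error.** If the observed TMIST share is used as the reference, the test rejects too often when the two shares are truly equal.
- **Power.** The 3.9-point figure contains no TMIST sampling error, so it is optimistic for a valid comparison of the two groups.
- **Size unknown.** Both effects depend on the TMIST n, which the plan does not give for this objective. Nor does it say whether section 7.3 would use all concurrent TMIST enrollees or the random sample drawn for section 7.4.

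Section 2.2.3 calls this a key hypothesis. A false positive could be read as evidence that WOC are over- or under-represented among women who decline.

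**Working it through.** **Inputs.** EAQ201 n = 1,000 (section 7.2; not restated in 7.3). TMIST share 0.25, difference 0.039, two-sided alpha 0.05 (section 7.3). TMIST n, written m, is not given and is therefore varied.

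**1. The plan's own figure.** Exact binomial test, n = 1,000, null 0.25 held fixed, at most 0.025 in each tail: reject if the WOC count is 222 or fewer, or 278 or more. The attained size is 4.45%. Power is 78.8% at a true share of 0.289 and 81.4% at 0.211. The stated 80% for 3.9 points is therefore reproduced, within rounding, with no TMIST sampling error.

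**2. Values of m.** Section 7.4 assumes EAQ201 women make up 0.20 to 0.50 of the analysis set, and Table 5 also shows 0.40. With 1,000 EAQ201 women and EAQ201 fraction s, m = 1,000 × (1 − s)/s:

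- s = 0.50: m = 1,000
- s = 0.40: m = 1,500
- s = 0.20: m = 4,000

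Of these, only m = 1,000 is printed in Table 5 against 1,000 EAQ201 women; the other two are rescaled from the ratios. As assumptions for a larger comparator, I add m = 10,000 and 50,000.

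**3. Type I error of the one-sample test with an estimated reference.** When both groups share the same true proportion, the variance of the difference is proportional to 1/1,000 + 1/m, but the test uses only 1/1,000. Hence

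type I error = 2 × [1 − Φ(1.96 / √(1 + 1,000/m))].

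For m = 1,000: 1.96/√2 = 1.386, giving 16.6%. For m = 4,000: 1.96/√1.25 = 1.753, giving 8.0%. The rate reaches 6% at m of about 11,600 and is lower beyond that. The plan's exact test was also evaluated by enumerating both groups at a true share of 25%.

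**4. Two-sample power.** Pooled z-test, 1,000 EAQ201 women against m TMIST women:

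power = Φ[(|p1 − p0| − 1.96·SE0) / SE1],

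where SE0 uses the pooled proportion and SE1 the separate proportions. For m = 1,000, p1 = 0.289 and p0 = 0.25: pooled proportion 0.2695, SE0 = 0.01984, SE1 = 0.01982, so (0.0390 − 0.0389)/0.01982 ≈ 0.005 and power is 50%.

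| TMIST n (m) | One-sample type I, z | One-sample type I, exact | Two-sample power, 28.9% vs 25% | Two-sample power, 21.1% vs 25% | Increase detectable at 80% power |
|---|---|---|---|---|---|
| 1,000 | 16.6% | 15.8% | 50% | 54% | 5.6 points |
| 1,500 | 12.9% | 12.2% | 58% | 62% | 5.1 points |
| 4,000 | 8.0% | 7.4% | 71% | 74% | 4.4 points |
| 10,000 | 6.2% | 5.7% | 76% | 79% | 4.1 points |
| 50,000 | 5.2% | 4.8% | 79% | 82% | 3.9 points |

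Fisher's exact test is slightly less powerful for the increase: 48%, 56%, 69% and 75% at m = 1,000, 1,500, 4,000 and 10,000.

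**The case against.** The strongest reply is that TMIST is the parent trial and nothing in section 7.3 says a sample will be drawn from it. Random selection belongs to section 7.4 and a different objective. If the full TMIST share is the benchmark and m runs to tens of thousands, the one-sample test is a usable approximation. That stands as far as it goes: the table shows almost no harm at 50,000. But the plan does not say that all TMIST women are used. Section 5 restricts the comparator to the same time period, and also expects EAQ201 enrollment to finish within a few months. The concurrent group may therefore be much smaller than the whole trial.

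A second reply is that 25% is a fixed benchmark. The text presents it as an approximate figure from TMIST data, which reads as a planning value. Testing against it would also answer a different question from objective 2.2.3.

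Third, section 7.2 reports 16% WOC among decliners. Against 25%, a two-sample z-test has about 99.9% power even at m = 1,000, so the loss of power may not matter in practice. That is fair on power at that gap. It does not repair the false-positive rate when the shares are close, nor the stated 3.9-point figure. The 16% also lies in the opposite direction to the hypothesis in section 7.1.2.3, so it is not a secure guide to the expected effect.

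Finally, the calculations assume independent women and simple random sampling. The selection in section 7.4 is stratified by site and enrollment time, so the figures for that scenario are approximate.

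**Conclusion.** The concern holds, and it is minor. The plan uses a one-sample test for a comparison of two observed groups and gives no TMIST n for it. The stated power is correct only if the TMIST share is known exactly. If the observed share is used as the reference, the normal-approximation type I error ranges from about 5.2% with 50,000 TMIST women to 16.6% with 1,000, and two-sample power for a 3.9-point increase ranges from 79% down to 50%. These figures rest on 1,000 EAQ201 women, a TMIST share of 25%, independent observations and assumed values of m. The wording gap is certain; the size of the harm cannot be fixed until the comparator is defined.

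**What to change.** In section 7.3, replace the one-sample test with a two-sample proportion test of EAQ201 against concurrent TMIST participants, using the observed TMIST share and not 25%. The section already names this family of tests for its other secondary comparisons. A logistic model with site and enrollment time is an alternative, but its power was not calculated here. State which TMIST women form the comparator, over what period, and how many, and restate the power or detectable difference for that number. As a side item, say that one WOC definition applies to both groups, including how Hispanic White women are classed.

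The cost is wording in the statistical section, with no new data. The stated detectable increase may become less favorable: about 3.9 points, as now, if the comparator is near 50,000, but 4.4 at 4,000 and 5.6 at 1,000.
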